#### List of Abbreviations:

	<del>-</del>
AE	Adverse event
AESI	Adverse event of special interest
SAE	Serious adverse event
PCV13	Pneumococcal conjugate vaccine, 13 valent
4CMenB	4 component MenB protein vaccine, (Bexsero®)
PO	Primary objective
SO	Secondary objective

### 1. Introduction

#### 1.1. Trial Details

*Neisseria meningitidis* serogroup B (MenB) causes the majority of meningococcal disease in the UK where infants have the highest incidence. The 4CMenB vaccine (Bexsero®) can protect infants against MenB after at least two priming doses. The UK schedule currently offers a two-dose priming regime at 2 and 4 months with a booster at 12 months.

An earlier schedule may prevent more cases of MenB. This study aims to compare the immune responses of UK infants who receive their routine immunisations alongside two different 4CMenB primary immunisation schedules. Full rationale can be found in the protocol.

### 1.2. Person responsible for the statistical analysis

[name], Statistics Unit, UK Health Security Agency (UKHSA). The analysis may be performed under supervision of the responsible statistician.

### 1.3. Changes to the analysis plan

A final version of this plan will be produced prior to provision of data to the statistician. Any additional analysis or deviation(s) from this analysis plan will be documented and the reasons given in appendix 1 of this document.

## 2. Trial Design Summary

This is a multicentre, open label, phase IV study at several participating NHS sites in England. Term, healthy infants (born at  $\geq$ 37 weeks gestation), aged  $\geq$ 56 days to  $\leq$  70 days are randomised to one of two 4CMen B schedules:

- Group 1: 4CMenB Bexsero® at 2, 3 and 12 months of age; PCV13 at 4 months of age
- Group 2: 4CMenB Bexsero® at 2, 4 and 12 months of age; PCV13 at 3 months of age

All other routine immunisations are received alongside the above allocation, as per the UK vaccination schedule. Infants remain in the study from recruitment to around 13 months of age with blood sample schedule as below. After each vaccination visit, parents/caregivers complete a 7 day paper diary for collection of solicited AEs (temperature, redness, swelling, tenderness, feeding, activity, irritability, persistent crying, diarrhoea, vomiting). All other unsolicited AEs are collected at each visit by study staff. SAEs and AESIs are collected from the time of consent to last visit. AESIs for this study were: Febrile seizures, arthritis.

### 2.1. Study Visit Schedule

Simplified study visit procedures for groups 1 and 2 are shown below, for full study procedures see protocol.

Table 1 Study Procedures - Group 1 and 2

Visit Number	1	2	3	4	5	6
Age	2 months	3 months	4 months	5 months	12 months	13 months
Study Timeline	Day 0	V1 + 28 days	V2 +28 days	V3 + 28-days		V5 +28 days
Visit window		+14 days	+ 14 days	+ 14 days	+21 days	+ 21 days
Group 1	ACMenB DTaP/IPV/ Hib/HepB Rotavirus	4CMenB DTaP/IPV/ Hib/HepB Rotavirus	PCV13 DTaP/IPV/ Hib/HepB  Blood Sample 1		ACMenB PCV13 MCC-TT/ Hib-TT/MMR  Blood Sample 2	Blood Sample 3
Group 2	4CMenB DtaP/IPV/ Hib/HepB Rotavirus	PCV13 DtaP/IPV/ Hib/HepB Rotavirus	4CmenB DtaP/IPV/ Hib/HepB	Blood Sample 1	4CMenB PCV13 MCC-TT/ Hib-TT/MMR  Blood Sample 2	Blood Sample 3

### 2.2. Randomisation and blinding

Participants are randomised in a 1:1 ratio between groups 1 and 2. A computerised block randomisation list is produced for each site, placed inside an opaque envelope with corresponding participant number. At recruitment, each participant is allocated, in order of inclusion, the next available participant number from the randomisation. Prior to first vaccinations, the local study team will open the envelope and reveal the group number allocation and so vaccination schedule to be followed.

This is an unblinded study; both study teams and participants are aware of their allocation. However, laboratory staff testing the vaccine responses will be blinded to group allocation.

### 2.3. Supply of data

Data is entered from the paper source at sites into a secure, online, password access eCRF (MACRO) by delegated site staff. Data is cleaned, locked and then downloaded from this database and provided to the study statistician in Excel/CSV format for upload into STATA.

## 3. Sample Size

We propose that a comparison of 2 schedules with respect to doses of 4CMenB will require 60 infants in each arm. Based on data from a recent study (Gossger et al. 2012) the standard deviation of the GMT responses to the 3 antigens is expected to be around 1.0 loge units.

Therefore, in order to detect a 1.49 fold difference between groups at 80% power with 5% significance, and anticipating a 10% drop-out rate, we aimed to recruit 110 infants in each group, 220 in total. See protocol for further details.

# 4. Objectives

### 4.1. Primary objectives

PO1: To compare the immunological responses of UK infants at 28 days after the second dose (in blood sample 1) between two different primary immunisation schedules of 4CMenB (2, 3 vs. 2, 4 months of age).

### 4.2. Secondary objectives

SO1: To compare the persistence of immunological responses to 4CMenB at 12 months chronological age after two different primary immunisation schedules of 4CMenB (2, 3 vs. 2, 4 months of age).

SO2: To compare the immunological responses one month after the 12-month 4CMenB booster in infants who received two different primary immunisation schedules of 4CMenB (2, 3 vs. 2, 4 months of age).

SO3: To compare the persistence of immunological responses to PCV13 at 12 months chronological age after two different primary immunisation schedules of PCV13 (3 vs. 4 months of age).

SO4: To compare the immunological responses to the booster dose of PCV13 given at 12 months in infants who received two different primary immunisation schedules of PCV13 (3 vs. 4 months of age).

### 4.3. Safety objectives

- 1. To describe the safety of 4CMenB when given concomitantly with routine vaccines at 2 and 3 months of age (Group 1).
- 2. To describe the safety of 4CMenB when given concomitantly with routine vaccines at 2 and 4 months of age (Group 2).
- 3. To describe the safety of PCV13 when given concomitantly with routine vaccines at 3 months of age (Group 2).
- 4. To describe the safety of PCV13 when given concomitantly with routine vaccines at 4 months of age (Group 1).
- 5. To describe the safety of 4CMenB booster when given concomitantly with routine vaccines at 12 months of age (Group 1 and 2).
- 6. To describe the safety of PCV13 booster when given concomitantly with routine vaccines at 12 months of age (Group 1 and 2).

### 5. Outcome Measures

### 5.1. Primary end points

Objective	Outcome Measures
To compare the immunological responses of UK infants between two different primary	1. Antibody titres against relevant 4CMenB antigens (fHbp, NadA and PorA) measured by serum bactericidal assay using human complement (hSBA) 4 weeks after 2nd dose of 4CMenB (blood sample 1 at 4 months of age for Group 1 versus 5 months of age for Group 2).
immunisation schedules of 4CMenB (2 and 3 versus 2 and 4 months of age).	
 
Antibody titres ≥ 1:4 against relevant 4CMenB antigens (fHbp, NadA and PorA) measured by hSBA assessed at 4 weeks after 2nd dose of 4CMenB (blood sample 1 at 4 months of age for Group 1 versus 5 months of age for Group 2).
 

# 5.2. Secondary end points

Objective	Outcome Measures		
To compare the persistence of immunological responses to 4CMenB at 12 months chronological age after two		Antibody titres against relevant 4CMenB antigens (fHbp, NadA and PorA) measured by hSBA at 12 months of chronological age (blood sample 2, pre-booster).	
different primary immunisation schedules of 4CMenB (2 and 3 versus 2 and 4 months of age).	2.	Antibody titres ≥ 1:4 against relevant 4CMenB antigens (fHbp, NadA and PorA) measured by hSBA at 12 months of chronological age (blood sample 2, pre booster).	
To compare the immunological responses one month after the 12-month 4CMenB booster in infants who received two different	1.	Antibody titres against relevant 4CMenB antigens (fHbp, NadA and PorA) measured by hSBA at 13 months of chronological age (blood sample 3, 4 weeks post-booster).	
primary immunisation schedules of 4CMenB (2 and 3 versus 2 and 4 months of age).	2.	Antibody titres ≥ 1:4 against relevant 4CMenB antigens (fHbp, NadA and PorA) measured by hSBA at 13 months of chronological age (blood sample 3, 4 weeks post booster).	
To compare the persistence of immunological responses to PCV13 at 12 months chronological age after two different primary	1.	Serotype specific antibody concentrations against PCV13 serotypes at 12 months of age (blood sample 2, pre PCV13 booster).	
immunisation schedules of PCV13 (3 versus 4 months of age).	2.	Antibody concentrations $\geq$ 0.35 µg/ml against PCV13 serotypes at 12 months of age (blood sample 2, pre PCV13 booster).	
To compare the immunological responses to the booster dose of PCV13 given at 12 months in infants who received two different	1.	Serotype specific antibody concentrations against PCV13 serotypes at 13 months of age (blood sample 3, 4 weeks post PCV13 booster).	
primary immunisation schedules of PCV13 (3 versus 4 months of age).	2.	Serotype-specific antibody concentrations $\geq$ 0.35 µg/ml against PCV13 serotypes at 13 months of age (blood sample 3, 4 weeks post PCV13 booster).	

# 5.3. Observational end points: Safety data

Objective	Outcome Measures
-----------	------------------

To describe the safety of 4CMenB when given concomitantly with routine vaccines at 2 and 3 months of age (Group 1).

To describe the safety of 4CMenB when given concomitantly with routine vaccines at 2 and 4 months of age (Group 2).

To describe the safety of PCV13 when given concomitantly with routine vaccines at 3 months of age (Group 2).

To describe the safety of PCV13 when given concomitantly with routine vaccines at 4 months of age (Group 1).

To describe the safety of 4CMenB booster when given concomitantly with routine vaccines at 12 months of age (Group 1 and 2).

To describe the safety of PCV13 booster when given concomitantly with routine vaccines at 12 months of age (Group 1 and 2).

- 1. Occurrence, nature, time of onset, duration, intensity, action taken and whether the event led to early termination from the study, of any solicited AEs within 7 days after each vaccination(s).
- 2. Occurrence, nature, time of onset, duration, intensity, action taken and whether the event led to early termination from the study, of any unsolicited AEs within 28 days after each vaccination(s).
- 3. Occurrence, nature, time of onset, duration, intensity, action taken and whether the event led to early termination from the study, of any medically attended AEs for the whole duration of the study.
- 4. Occurrence, nature, time of onset, duration, intensity, action taken, relationship to vaccination, outcome and whether the event led to early termination from the study, of any SAEs and AESIs for the whole duration of the study.

# 6. Analysis sets, missing data, censored data, significance level

### 6.1. Analysis sets

Data will be analysed using a modified intention to treat (mITT) analysis: all infants vaccinated, and with a blood sample taken and with antibody results available for the relevant end point will be included and analysed according to their randomised group. The mITT analysis will include blood samples taken outside the recommended timing.

Per protocol analysis (whereby all vaccinated infants with at least one post vaccination blood sample taken and with no major protocol deviations) may also be performed if major protocol deviations are recorded in more than 5% of subjects. This will be specified in the report.

#### 6.1.1. Major protocol deviation definitions

A major protocol deviation will be defined as:

- Incorrect vaccination schedule given per randomisation group for either 4CMenB or PCV13 vaccines any samples after this deviation occurs will be excluded from a per protocol analysis
- Incorrect number of doses of vaccine given for either 4CMenB or PCV13 any blood samples after this deviation occurs will be excluded from a per protocol analysis

- Vaccine doses given at more than 12 weeks before or after the intended age for either 4CMenB or PCV13 vaccines any samples after this deviation occurs will be excluded from a per protocol analysis
- Post vaccination blood sample (blood samples 1 and 3) obtained within 14 days of vaccination date or more than 56 days after vaccination date. This sample will be excluded from a per protocol analysis
- Pre booster blood sample (blood sample 2) obtained before 11 months of age or after 15 months of age. This sample will be excluded from a per protocol analysis

#### 6.2. Missing and censored data

Reasons for all missing and censored data will be reported but missing data will not be imputed. Missing data (e.g. from withdrawals, non-compliers) is assumed missing at random. Infants with missing results (e.g. unable to obtain or insufficient blood sample) at the different time-points (e.g. post-primary immunisation, pre-booster and post-booster) will not be included in the analysis for that particular time-point. Spurious data will be checked to source records and investigated, but included if no cause is identified.

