### 8.3. Immunogenicity analysis

### 8.3.1. Primary end-point analysis

For each vaccination schedule, GMTs of the hSBA titres to the three analysed 4CMenB antigens (fHbp, NadA and PorA) will be calculated with 95% confidence intervals. Schedules will be compared using unpaired t-tests on log-transformed titres or the Kruskal Wallis test if log-titres are not normally distributed. Proportions with titres ≥1:4 will also be calculated with exact binomial 95% confidence intervals and compared between groups by Fisher's exact test. Significance will be at a 5% level with no adjustment for multiple comparisons since whilst there are three antigens there are only two groups being compared.

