### 8.3.2. Secondary end-point analysis

This will be done in the same way as the primary end-point analysis described in 8.3.1. In addition, the geometric mean fold change between time points will be calculated with 95% confidence intervals.

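### Missing results are assumed missing at random, but the 12- and 13-month 4CMenB comparisons use unadjusted available-case tests that ignore the sample 1 titre; a joint model should be a named sensitivity analysis

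*SAP*

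**What the plan says.** Section 6.2 of the SAP makes one statement about the mechanism: "Missing data (e.g. from withdrawals, non-compliers) is assumed missing at random". It does not say which observed variables this is conditional on. The same section rules out imputation ("Reasons for all missing and censored data will be reported but missing data will not be imputed") and says that infants without a result "will not be included in the analysis for that particular time-point".

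Section 6.1 builds the same restriction into the mITT set: vaccinated infants "with a blood sample taken and with antibody results available for the relevant end point will be included".

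Section 8.3.1 gives the tests. For titres: "Schedules will be compared using unpaired t-tests on log-transformed titres or the Kruskal Wallis test if log-titres are not normally distributed". Proportions above the threshold are "compared between groups by Fisher's exact test". For the secondary end points, section 8.3.2 says: "This will be done in the same way as the primary end-point analysis described in 8.3.1". It adds only fold changes between time points.

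Section 8.3.3 describes an exploratory regression on logged titres. It adjusts for interval from vaccination to blood and for demographic factors, with gestation, age at first vaccination and sex as examples. No earlier titre is named, and no missing-data sensitivity analysis is specified.

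**The concern.** Missing at random allows loss to depend on anything observed. At 12 and 13 months, the observed variable most likely to predict the missing titre is the same infant's sample 1 titre. A two-group test on the infants who remain makes no use of it. If infants with low sample 1 titres are lost more often in one arm, those remaining in that arm are a selected, higher-titre subset. The difference in log GMT then carries the selection as if it were a schedule effect. A likelihood model of the repeated titres is valid under the assumption that section 6.2 states; the planned tests are not protected in the same way.

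At stake are SO1 (persistence at 12 months) and SO2 (response after the booster), where a spurious difference, or a masked one, could be reported. The trial is open label. In Table 1, sample 1 falls on a vaccination visit in Group 1 and on a blood-only visit in Group 2. Unequal loss is therefore plausible, but the SAP does not show that it will occur.

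**Working it through.** **Inputs from the SAP (section 3, Sample Size; section 2.2; section 6.3).** SD 1.0 on the log_e scale; 1.49-fold difference; 80% power; 5% significance, taken as two-sided; 10% drop-out; 110 per group; 1:1 allocation.

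**The plan's own figure.** n = 2(1.96 + 0.842)² × 1.0² / (ln 1.49)² = 2 × 7.85 / 0.3988² = 98.7, so 99 evaluable per group. 99 / 0.90 = 110. The planned 110 is reproduced, so these inputs are a fair base.

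**Assumed inputs, not in the SAP.** Correlation ρ between sample 1 and later log titre, 0.3 to 0.8. Strength of dependence of loss on sample 1 titre: odds ratio 2 per SD, or a logit slope of -1 per SD (low titres lost more often). Loss of up to 30%.

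**Formulas, with no true difference.** Let m be the mean standardised sample 1 titre among infants still observed in an arm, obtained by integrating a normal density over the logistic probability of remaining. Then:
- bias b = ρ(m₂ - m₁) in log_e units, because SD = 1
- apparent GMT ratio = exp(b)
- SE = √(1/n₁ + 1/n₂), with n₁ and n₂ the numbers observed
- type I error = Φ(-1.96 - b/SE) + 1 - Φ(1.96 - b/SE)

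**About 10% loss, dependence in one arm only.**
- Odds ratio 2 (higher titres lost more often), 10% loss in both arms: m = -0.066. ρ = 0.3 gives b = -0.020 and ratio 0.98; ρ = 0.7 gives b = -0.046 and ratio 0.955. Type I error is 5.2-6.2%.
- Slope -1: m = 0.091. ρ = 0.6 gives b = 0.054 and ratio 1.056; ρ = 0.8 gives b = 0.073 and ratio 1.075.

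The ratio is therefore roughly 2-8% away from 1.

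**20% loss in one arm (slope -1), 5% random loss in the other.** m = 0.173. ρ = 0.8 gives b = 0.139 and ratio 1.149. SE = √(1/104.5 + 1/88) = 0.145, b/SE = 0.96, and type I error is about 16%. Across 10-20% loss and ρ 0.6-0.8, simulated trials of 110 per group gave ratios of 1.06-1.15 and type I error of 6.6-17%. The likelihood model returned 1.00.

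**Other patterns (odds ratio 2, ρ 0.3 to 0.7).**

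| Loss | GMT ratio | Type I error |
|---|---|---|
| 10% in both arms, opposite dependence | 0.96 to 0.91 | 5.9-10.0% |
| 20% in both arms, dependence in one only | 0.96 to 0.91 | 5.8-9.2% |
| 10% v 30%, same dependence | 0.96 to 0.92 | 5.7-8.8% |
| 30% in both arms, opposite dependence | 0.89 to 0.77 | 10.9-37.8% |
| Same rate and same dependence | 1.00 | 5.0% |

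In the last row m₁ = m₂, so b = 0. Each group's own GMT is still shifted by ρm.

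**Does using the sample 1 titre remove the bias?** In six simulated scenarios (10-30% loss, ρ 0.5 or 0.7) conditioning on it left a bias of at most 0.002 log_e and type I error of 4.7-5.5%. The unadjusted test gave bias of up to 0.27 log_e in size and type I error of 5.2-39%.

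**Sample 1 itself.** If 11 of 110 infants lack sample 1 but all have a later sample, effective n = 99 / (1 - ρ² × 0.10). That is 100.6 at ρ = 0.4 and 105.8 at ρ = 0.8, a modest gain in precision.

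**The case against.** The strongest reply is that section 6.2 never says what the assumption is conditional on. The planned tests contain only group, so it may mean missing at random given group, and under that the tests are valid. That is a possible reading, but it turns the assumption into missing completely at random within group. That is stronger than the words used, and the plan should say so if it is meant.

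A reader might infer that the planned tests are valid only if loss is completely random within group. For the between-group comparison the documents do not support this: equal mechanisms and rates cancel. A reader might also take the differing visit burden at sample 1 as evidence of bias. It is not. Loss that depends on group alone leaves the comparison unbiased, and the SAP shows no route by which a titre unknown to the family would drive withdrawal.

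It is also fair that the larger figures come from unfavourable scenarios with assumed inputs, and that the bias at the planned 10% is small against the 1.49-fold design difference. The plan does promise reasons for missing data, a CONSORT flowchart and an adjusted regression in 8.3.3. That regression helps only partly: it is exploratory and names no earlier titre.

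Finally, a linear mixed model does not reach the threshold end points, and section 8.3.1 itself foresees log titres that are not normal. Both limits stand. They argue for a sensitivity analysis rather than a replacement.

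**Conclusion.** The stated assumption and the planned method do not match, and the mismatch matters for SO1 and SO2. If loss depends on the sample 1 titre and differs in mechanism or rate between arms, the GMT comparison is biased. At about 10% loss with dependence in one arm the ratio is off by roughly 2-8%. It is about 1.15 at 20% loss in one arm with correlation 0.8, and further from 1 with heavy, opposite loss. These sizes rest on assumed dependence, correlation and loss patterns; from the SAP come only the SD, the 10% drop-out and the group size.

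It would go too far to say that the primary result is at risk. No bias at sample 1 has been shown; the gain there is precision only, and only from infants who miss sample 1 but return later. This is a worthwhile, inexpensive improvement to the secondary analyses, not a flaw in the primary test.

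**What to change.** In section 6.2, state what missing at random is conditional on (for example group and the infant's other observed titres).

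In sections 6.2 and 8.3.2, pre-specify for each 4CMenB antigen a linear mixed model on log titre at samples 1, 2 and 3. Use group, time (sample number as a category) and group × time, with unstructured within-infant covariance, and include every infant with at least one result. Report the between-schedule GMT ratio with 95% CI at samples 2 and 3 beside the available-case test, as a named sensitivity analysis for SO1 and SO2. For each PCV13 serotype, model samples 2 and 3 jointly. Leave the primary sample 1 test as planned.

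Sample 1 should enter as an outcome in the joint model rather than as a covariate. It is measured after randomisation, so adjusting for it would change the question if the schedules differ at that point.

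Cost: SAP wording and one standard Stata model per antigen or serotype, with no new data. Downsides to record: the model relies on approximately normal log titres and on a correctly specified relation between earlier and later titres. It suits the data less well if many titres sit at the assay floor. It leaves the ≥1:4 and ≥0.35 µg/ml proportions unaddressed. The change should be made before data reach the statistician, as section 1.3 requires of the final plan.

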### 6.3. Significance level and confidence intervals

2-sided 95% confidence intervals will be reported. Where comparisons are made between groups a 5% significance level will be used.

## 7. Interim Analysis

No interim analysis is planned as all vaccines used in this trial are licensed for routine use in infants.

### 8. Statistical Methods

### 8.1. Statistical package

Stata version 17 or 18 will be used for analysis with Excel and GraphPad Prism as required.

#### 8.2. Descriptive analysis

At the end of the study, a flowchart will summarise the number of infants approached, consented, recruited, assigned to the different study arms, receiving the intended vaccines, completing the study protocol and analysed for the primary outcome, as recommended by the CONSORT statement (http://www.consort-statement.org/).

Baseline data comparing the two trial arms will be summarised in a table format and will compare median gestational age at birth, age at first vaccination, gender, recruiting study site, birth weight, underlying medical conditions, and relevant concomitant medications or vaccines. Proportion of infants receiving vaccinations and blood tests within protocol specified windows will be summarised for each group.

